#### Recording Adverse Events

The Investigator is responsible for recording all SAEs and only AEs related to study procedures that are observed or reported by the patient during the run-in period (before the administration of the first dose of study drug) regardless of their relationship to study drug through the end of study. All AEs, including non-serious AEs, occurring after signing of the ICF and before study

drug administration will be captured as medical history (see Section 6.1). All AEs will be collected starting after administration of the first dose through the end of the safety follow-up period. Non-serious AEs will be followed until the end of study.

The Investigator is responsible for recording SAEs that are observed or reported by the patient after the time when the informed consent is signed regardless of their relationship to study drug through the end of study. SAEs will be followed until satisfactory resolution, until baseline level is reached, or until the SAE is considered by the Investigator to be chronic or the patient is stable, as appropriate.

All AEs must be recorded in the source records for the clinical study center and in the eCRF for the patient, whether or not they are considered to be drug-related. Each AE must be described in detail: onset time and date, description of event, severity, relationship to study drug, action taken, and outcome (including time and date of resolution, if applicable).

For SAEs, record the event(s) on both the eCRF and the SAE form.

For AEs that are considered AEs of clinical interest (Section 6.7.6.1), the supplemental AEs of Clinical Interest eCRF should be completed. Additional clinical and laboratory information may be collected. Refer to CRF completion guidelines for details on reporting events in the supplemental AEs of Clinical Interest eCRF.

For all ISRs, the Investigator, or delegate, should submit a supplemental ISR eCRF, recording additional information (eg, descriptions, onset and resolution date, severity, treatment given, event outcome).

#### **6.7.6.3. Reporting Adverse Events of Clinical Interest to Sponsor/Designee**

For AEs that are considered AECIs (Section 6.7.6.1), the Sponsor or its designee should be notified within 24 hours using a supplemental AEs of Clinical Interest eCRF.

#### **6.7.6.4. Serious Adverse Events Require Immediate Reporting to Sponsor/Designee**

An assessment of the seriousness of each AE will be made by the Investigator. Any AE and laboratory abnormality that meets the SAE criteria in Section 6.7.6.1 must be reported to the Sponsor or designee within 24 hours from the time that clinical study center staff first learns of the event. All SAEs must be reported regardless of the relationship to study drug.

The initial report should include at least the following information:

- Patient's study number
- Description and date of onset of the event
- Criterion for serious
- Preliminary assignment of relationship to study drug, and
- Investigator/site information

To report the SAE, complete the SAE form. Within 24 hours of receipt of follow-up information, the Investigator must update the SAE form. SAEs must be reported using the contact information provided in the Investigator Site File.

Appropriate remedial measures should be taken by the Investigator using his/her best medical judgment to treat the SAE. These measures and the patient's response to these measures should be recorded. All SAEs, regardless of relationship to study drug, will be followed by the Investigator until satisfactory resolution or the Investigator deems the SAE to be chronic or stable. Clinical, laboratory, and diagnostic measures should be employed by the Investigator as needed to adequately determine the etiology of the event.

#### **6.7.6.5. Sponsor Safety Reporting to Regulatory Authorities**

The Sponsor or its representative will report certain study events in an expedited manner to the Food and Drug Administration, the European Medicines Agency's EudraVigilance electronic system according to Directive 2001/20/EC, and to all country Regulatory Authorities where the study is being conducted, according to local applicable regulations.

#### **6.7.6.6. Serious Adverse Event Notification to the Institutional Review Board/Independent Ethics Committee**

Suspected unexpected serious adverse reactions (SUSARs) will be reported to the IRB/IEC per their institutional policy by the Investigator or Sponsor (or Sponsor designee) according to country requirements. Copies of each report and documentation of IRB/IEC notification and acknowledgement of receipt will be kept in the Investigator's study file.

#### **6.7.6.7. Pregnancy Reporting**

If a female patient becomes pregnant during the study through 90 days following the last dose of study drug, the Investigator must report the pregnancy to the Sponsor or designee within 24 hours of being notified of the pregnancy. Details of the pregnancy will be recorded on the pregnancy reporting form. The patient should receive any necessary counseling regarding the risks of continuing the pregnancy and the possible effects on the fetus.

The pregnancy should be followed by the Investigator until completion. At the completion of the pregnancy, the Investigator will document the outcome of the pregnancy. If the outcome of the pregnancy results in a postpartum complication, spontaneous abortion, stillbirth, neonatal death, or congenital anomaly, then the Investigator should follow the procedures for reporting an SAE as outlined in Section 6.7.6.4.

#### **6.7.6.8. Overdose Reporting**

An overdose is defined as any dose administered to or taken by a patient (accidentally or intentionally) that exceeds the highest daily dose, or is at a higher frequency, than included in the protocol. The investigator will decide whether a dose is to be considered an overdose, in consultation with the Sponsor. In the event of an overdose, the actual dose administered must be recorded in the eCRF.

All reports of overdose (with or without an AE) must be reported within 24 hours to the Sponsor or designee.

## 6.8. Biomarkers, DNA Genotyping, and Biospecimen Repository

Alnylam's RNAi therapeutics platform permits the highly specific targeting of investigational therapies based on genetic sequence. It is possible that variations in the target genetic sequence will result in variations in drug effect.

More generally, genetic variations may account for the well-described heterogeneous manifestations of disease in patients with IgAN, as well as their responses to treatment.

To permit exploratory investigations and the application of novel approaches to bioanalyses that may further elucidate the outcomes of this study, or potentially advance understanding of the safety, mechanism of action, and/or efficacy of cemdisiran, a set of biological specimens will be collected at the intervals indicated in the Schedule of Assessments ([Table 1](#) and [Table 2](#)).

The biospecimen repository will also include residual material from routine samples (safety laboratory samples, PK samples, etc.) that are obtained during the study.

These specimens will be securely stored in a central biorepository for up to 10 years following the completion of this clinical study (ie, last patient last visit), or as per local regulations. After 10 years have elapsed, samples will be destroyed.

Where allowed per local regulations, ethics committee (IRB/IEC) approval, and patient consent, the samples will be collected as part of this study. Examples of potential exploratory investigations would include DNA, RNA or biochemical metabolite assessments as they relate to disease progression, efficacy or safety.

Details regarding the collection, processing, storage, and shipping of the samples will be provided in the Laboratory Manual.

Exploratory analysis of these biospecimens will be performed by Alnylam Pharmaceuticals or its designees.

When biobanking is permitted by local regulation, study participants will be advised during the informed consent process of these biobanking details and the potential for exploratory investigation of their samples.

## 7. STATISTICS

A Statistical Analysis Plan (SAP) will be finalized before database lock. The plan will detail the implementation of the statistical analyses in accordance with the principle features stated in the protocol.

### 7.1. Determination of Sample Size

Approximately 30 patients are planned to be randomized 2:1 (cemdisiran:placebo) in this study. This is based on the assumption that, in the placebo arm, the estimated geometric mean ratio of proteinuria at Week 32 to baseline is 0.88 (log standard deviation [SD] 0.597), corresponding to a 12% reduction. A sample size of 27 with 2:1 randomization (cemdisiran:placebo) will provide a width of 0.80 for the 90% confidence interval (CI) for treatment effect size estimate (cemdisiran – placebo) in log scale. This corresponds to a 90% CI of (15%, 62%) for the treatment difference in the percentage scale if the true Week 32 reduction is 50% for the cemdisiran arm. To account for potential dropouts, approximately 30 patients are planned to be randomized stratified by baseline urine protein levels ( $\geq 1$  g/24h and  $< 2$  g/24h versus  $\geq 2$  g/24h).

### 7.2. Statistical Methodology

The statistical and analytical plans presented below are brief summaries of planned analyses. More complete plans will be detailed in the statistical analysis plan (SAP). Changes to the methods described in the final SAP will be described and justified as needed in the clinical study report. For information on study endpoints, see Section 2.

#### 7.2.1. Populations to be Analyzed

The following populations will be analyzed:

- Modified Intent-to-treat (mITT): All patients who receive any amount of study drug and have at least one post baseline assessment in proteinuria. Patients will be grouped by assigned treatments (ie, as randomized).
- Safety Analysis Set: All patients who received any amount of study drug. Patients who received any amount of cemdisiran will be included in the cemdisiran arm. Patients in the Safety Analysis Set will be grouped by treatment received.
- PK Analysis Set: All patients who receive any amount of study drug and have at least one postdose blood or urine sample for PK concentration.
- PD Analysis Set: All patients who receive any amount of study drug and who have at least one postdose blood sample for the determination of plasma C5 level.

The primary population used to evaluate efficacy will be the mITT Population. Sensitivity analyses for efficacy will be performed using the Per Protocol Analysis Set. Safety will be analyzed using the Safety Analysis Set. The PK and PD Analysis Sets will be used to conduct PK and PD analyses, respectively.

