### 3. INVESTIGATIONAL PLAN

#### 3.1. Summary of Study Design

This is a multicenter, double-blind, placebo-controlled study comprised of three periods ([Figure 1](#)). The first period of the study is an observational 14-week run-in period during which patients' blood pressure, kidney function, degree of hematuria, and proteinuria will be measured. Patients will not receive study drug (cemdisiran or placebo) during this time. The standard of care is expected to remain unchanged during this run-in period. The second study period is a 36-week treatment period which will evaluate the efficacy and safety of SC cemdisiran compared to SC placebo in combination with standard of care in patients with IgAN and persistent proteinuria. The third period of the study is a 52-week optional open-label extension (OLE) period to further evaluate the long-term safety and clinical activity of cemdisiran. During the OLE, all patients (including those initially on placebo) will be treated with cemdisiran in combination with standard of care.

The study will include Screening of up to 90 days to determine eligibility of patients and to complete disease-related assessments. Patients will provide written informed consent and visit the study center approximately 2 weeks before starting the run-in period to complete the protocol screening assessments. Following successful screening, the 14-week run-in period will commence, during which patients' blood pressure, kidney function, degree of hematuria and proteinuria as well as treatment with standard of care will be documented by the Investigator. The standard of care is expected to remain unchanged during this run-in period. Patients whose proteinuria level remains  $\geq 1$  g/24-hours within 2 weeks of the end of the run-in period, and who meet blood pressure and eGFR criteria will be eligible to enroll in the 36-week treatment period. Upon confirmation of eligibility followed by vaccination against meningococcal infections, patients will be randomized at a 2:1 ratio to receive 600 mg of cemdisiran or placebo every 4 weeks in combination with standard of care. Approximately 30 patients are planned to be randomized in total, 20 in the cemdisiran arm and 10 in the placebo arm. Patients excluded before randomization will be replaced at Screening.

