During the run-in period, patients will visit the study center 14, 8, and 2 weeks prior to randomization (Weeks 0, 6 and 12 of the run-in period). Patients will then return to the study center every 4 weeks after the start of study drug treatment period. The primary endpoint will be assessed at the end of treatment at Week 32.

At the end of treatment (Week 32), patients in the two treatment arms will enter the optional OLE period where they will receive cemdisiran at a dose of 600 mg every 4 weeks in combination with standard of care for 52 weeks. The first study drug administration of the OLE will be administered at Week 36. Patients will return to the study center at Week 40 and every 8 weeks thereafter during the OLE. Home visits, where locally feasible, may be arranged for cemdisiran administration in between 8-weekly study center visits (Weeks 44, 52, 60, 68 and 76), unless patients are required to visit the study center as judged necessary by the Investigator, or if home visits cannot be arranged. An end of treatment (EOT) visit will occur at Week 80 (OLE EOT) and an end of study (EOS) or early termination (ET) visit will be completed at Week 84 (OLE EOS/ET). For patients who complete the treatment period only who do not consent to continue to participate in the study in the OLE period, the EOS/ET visit will be at Week 36.

Patients will return to the clinical study center for safety follow-up visits approximately 13, 26, 39 and 52 weeks after the EOS/ET visit (regardless if EOS/ET visit is at Week 36 or Week 84), unless enrolled in another study with cemdisiran. Home visits, where locally feasible, may be arranged during safety follow-up at 13 and 39 weeks after the EOS/ET visit (regardless if EOS/ET visit is at Week 36 or Week 84).

Regular reviews of safety and tolerability data will be performed by an independent data monitoring committee (DMC) throughout the study with the primary purpose of protecting the safety of participating patients and the integrity of the study.

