#### 7.2.8. Safety Analyses

The primary parameter is the frequency of treatment-emergent AEs (hereafter referred to simply as AEs). Safety parameters also include vital signs, ECGs, clinical laboratory assessments, and physical exams. The extent of exposure will be summarized by dose level and overall.

Adverse events will be classified according to the Medical Dictionary for Regulatory Activities (MedDRA) System Organ Class and Preferred Term. Prior and concomitant medications will be classified according to the World Health Organization (WHO) drug dictionary. All SAEs occurring before the first dose of study drug and AEs related to study procedures will be listed. The number and percentage of patients experiencing AEs after the first dose of the study drug or events that worsened in severity after dosing will be summarized. AEs will be presented by maximum severity and relationship to study medication. SAEs and AEs leading to discontinuation of treatment will also be tabulated.

By-subject listings will be provided for deaths, SAEs, and AEs leading to study discontinuation.

Frequency of adverse events of clinical interest will also be summarized and by-subject listings will be provided.

Descriptive statistics will be provided for clinical laboratory data, 12-lead ECG interval data and vital signs data, presented as both actual values and changes from baseline over time. Laboratory shift tables from baseline to worst values will be presented. Baseline will be defined as the last observation on or prior to Study Day 1.

Abnormal physical examination findings and 12-lead ECG data will be presented in a by-patient data listing. Details of any abnormalities will be included in patient listings.

Other safety summaries will be presented as appropriate. Further details will be specified in the SAP.

All safety analyses will be conducted using the Safety Analysis Set.

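### The Safety Analysis Set arm rule has no period limit, so placebo patients who enter the open-label extension are counted, with their placebo-period events, in the cemdisiran arm

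*Protocol*

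**What the plan says.** Section 7.2.1 defines membership: "Safety Analysis Set: All patients who received any amount of study drug". It then fixes the arms: "Patients who received any amount of cemdisiran will be included in the cemdisiran arm", and "Patients in the Safety Analysis Set will be grouped by treatment received". None of these sentences names a study period.

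Section 7.2.8 ends: "All safety analyses will be conducted using the Safety Analysis Set". It summarizes the number and percentage of patients with adverse events after the first dose of study drug, without a stop at Week 36. It sets the laboratory baseline at the last value up to Study Day 1 and plans shift tables from there to the worst value. Section 6.7.6.2 collects adverse events to the end of safety follow-up, so the extension is covered.

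Section 3.1 describes a "52-week optional open-label extension (OLE) period" and states: "During the OLE, all patients (including those initially on placebo) will be treated with cemdisiran in combination with standard of care". It also says: "The first study drug administration of the OLE will be administered at Week 36". On numbers: "Approximately 30 patients are planned to be randomized in total, 20 in the cemdisiran arm and 10 in the placebo arm".

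Section 2 lists adverse event frequency as a secondary endpoint.

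**The concern.** A rule that any exposure to the active drug places a patient in the active arm suits a parallel-group trial, where the only way for a placebo patient to receive active drug is a dosing error. Here the design itself gives cemdisiran to every placebo patient who continues.

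Three things follow if the rule is applied as written. Events that arose on placebo are reported under cemdisiran. The comparator shrinks with each patient who continues. The patients who remain as placebo are selected after randomization, because they declined the extension or left the study. Laboratory shift tables have the same fault: a continuing placebo patient's worst value may have occurred before any cemdisiran was given, yet it would appear under cemdisiran.

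At stake is the randomized, blinded comparison of adverse event frequency. Pooling can hide a true excess on cemdisiran as easily as it can charge the drug with events it did not cause.

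**Working it through.** The plan gives no figure of its own on this point beyond the 20:10 split. Its precision statement in Section 7.1 concerns proteinuria and does not bear on safety.

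**Inputs**
- Planned arms: 20 cemdisiran, 10 placebo (Section 3.1).
- Double-blind period: 36 weeks, first extension dose at Week 36 (Section 3.1).
- Extension uptake: optional and not stated. Assumed range 50% to 100% of placebo patients, so k = 5 to 10.

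**Step 1: arm sizes under the rule.** Cemdisiran = 20 + k; placebo = 10 − k. Share of the cemdisiran arm that was randomized to placebo = k/(20 + k). Placebo time relabelled = k × 36/52 patient-years.

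| Placebo uptake | Arms as analysed | Former placebo share | Placebo time relabelled |
|---|---|---|---|
| 50% (k = 5) | 25 vs 5 | 5/25 = 20% | 5 × 36/52 = 3.5 patient-years |
| 80% (k = 8) | 28 vs 2 | 8/28 = 29% | 8 × 36/52 = 5.5 patient-years |
| 100% (k = 10) | 30 vs 0 | 10/30 = 33% | 10 × 36/52 = 6.9 patient-years |

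**Step 2: direction of the distortion.** The protocol gives no adverse event rates. Assume, for illustration only, double-blind incidences of 50% on cemdisiran and 20% on placebo. The double-blind incidence shown for the cemdisiran arm is (20 × 0.5 + k × 0.2)/(20 + k):
- k = 5: 11/25 = 44%
- k = 8: 11.6/28 = 41%
- k = 10: 12/30 = 40%

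A true 50% would be reported as 40% to 44%.

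**Step 3: how much of the pooled time is mislabelled.** Suppose all 30 patients enter the extension and stay from Week 36 to Week 84 (48 weeks). True cemdisiran time is 20 × 36/52 = 13.8 patient-years double-blind plus 30 × 48/52 = 27.7 in the extension. With 6.9 relabelled, the pooled total is 48.4 patient-years before safety follow-up, and the mislabelled part is 6.9/48.4 = 14%.

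**Step 4: is the rule limited anywhere?** Reading Sections 7.2.1 and 7.2.8 against Sections 3.1 and 6.7.6.2, I find no double-blind safety set, no extension set and no grouping by period.

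**The case against.** The strongest defence is that the rule was meant only for dosing errors in the double-blind period. Section 3.1 uses the word arm for the randomized groups, the extension has one treatment and no arms, and grouping by treatment received could be read period by period. A rule that dissolves the placebo arm would also defeat Section 1.3 (seen here in its Amendment 1 text), which justifies that arm partly by better assessment of safety. I accept this as the probable intent. It does not cure the text: no section states the limit, and a programmer following Section 7.2.1 would not find it.

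A second defence is that Section 7.2 is a summary and that Section 7.2.8 leaves further details to the SAP. This stands for exposure-adjusted rates, the handling of unequal follow-up and table layout. A reader might infer that planning simple percentages over unequal follow-up is itself an error; that is commonly left to the SAP and is not one. It does not stand for arm assignment, which the protocol itself fixes.

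Third, safety is summarized descriptively with no planned test, the monitoring committee sees unblinded data (Section 3.7), and efficacy uses the mITT population grouped as randomized. All true, and they limit the consequence.

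Finally, the current synopsis and schedule tables are not among the pages at hand. The Amendment 1 synopsis carries the same sentence, also without a limit.

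**Conclusion.** The point holds as a drafting fault in a rule the protocol states itself. Read literally, Sections 7.2.1 and 7.2.8 relabel placebo-period safety data as cemdisiran data and reduce the randomized control from 10 to 10 − k. The size depends on extension uptake, which the protocol does not give; the 50% to 100% range is my assumption.

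Three stronger readings are tempting and are not supported:
- A reader might infer that the placebo arm disappears. That happens only at full uptake. Below that it shrinks and ceases to be a randomized group.
- A reader might set 5.5 to 6.9 relabelled patient-years (80% to 100% uptake) against 13.8 double-blind cemdisiran patient-years and conclude that the mislabelled part is around half as large as the true exposure. That omits extension exposure, which the same pooled analysis includes. With full uptake and completion the share is about 14% of pooled time. The damage lies in the lost comparison more than in that share.
- A reader might infer that safety is the main reason for the placebo arm. Section 1.3 also gives interpretation of efficacy, and the primary endpoint is a placebo comparison of proteinuria.

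Efficacy conclusions are not affected.

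**What to change.** In Section 7.2.1, limit the any-cemdisiran rule to dosing in the 36-week double-blind period, before the first extension dose. A placebo patient given cemdisiran in error before that point would still count as cemdisiran.

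In Section 7.2.8, base the between-arm safety summaries, including laboratory shift tables, on data before the first extension dose, or through Week 36 for patients who do not enter the extension. Summarize safety on cemdisiran, including the extension, separately, counting from each patient's first cemdisiran dose: Day 1 for those randomized to cemdisiran, the first extension dose (scheduled at Week 36) for those who cross over from placebo.

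Exposure adjustment and table layout can stay in the SAP. The cost is a few sentences and one extra set of safety tables; no additional data are needed.
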